Arm 2: For the sham condition, parameters will consist of the current being ramped up over 60 seconds until it reaches 1 mA and then stopped. This allows for the same scalp sensation for both the sham and active condition so that subject and experimenter will remain blinded. This ramp up for one minute and then stopped and off for 20 minutes will be given each 20-minute sham session to keep the timing and subjective experience similar to the active condition.

All HD-tDCS protocols for participants will be pre-programmed into the Neuroelectrics software. HD-tDCS protocols will be set by a PI ([name]) for each participant using an encrypted approach, labeling with the participant research identifier to conceal condition assignment. Aside from the PI, other study team members will be unaware of the HD-tDCS condition allocation to preserve blinding.

Randomization: Participants will be randomized at a ratio of 1:1 to receive active 1 mA and sham conditions. Randomization of HD-tDCS condition assignments will be generated by a digital program, and the assignments (Protocol 1 = active or 2= sham) recorded in an encrypted spreadsheet that only the PI ([name]) has access to.

Blinding: Participants will be informed that sham and active HD-tDCS will be used in the study, but they will be blinded to condition. Aside from the PI ([name]), other study team members who deliver HD-tDCS and perform assessments will be blinded to HD-tDCS condition. Both the subject and study personnel will complete a questionnaire to check if blinding was successful.

Sample size calculation: Pre-study power analyses were conducted for the most power intensive phase (Phase 1 - randomized controlled trial) using a clinically relevant effect size derived from our prior studies. A sample size of 20 provides 80% power to detect a $f = .27$ effect size for the analysis of the primary outcome using an analysis of covariance model, assuming the baseline covariate of performance explains $R^2 = .2$ and $\alpha = .05$. Given that both our and other's research without intervention suggests that effect sizes tend to be larger in EEG compared to cognitive measures, we expect the effect size of EEG outcomes to be at least equivalent to cognitive outcomes.

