General linear models (analysis of covariance) will be used to evaluate whether cognitive performance following all HD-tDCS sessions statistically differs between HD-tDCS conditions, covarying for pre-treatment scores. Mixed effects models will be used to examine for a significant interaction between HD-tDCS condition and time across the 3 outcome intervals. Participants with missing time points will not be excluded. Clinically meaningful change associated with HD-tDCS will also be assessed. Proportions of individuals with a 5+ standardized score increase (T-score) on each measure of cognitive functioning will be characterized and evaluated using chi-square analyses. Statistical significance will be set at $\alpha = .05$.

EEG behavioral data will be tested using mixed effects models to examine for a significant interaction between HD-tDCS condition and time. Group assignment (active vs sham) will be used as the between subject factor; Time Point and Condition will be two within subject factors. In the Binding task, Condition included retrieval versus non-retrieval trials, while in the Association task, Condition included associated versus not-associated trials. Statistical significance will be corrected for the multiple electrode-time tests that will be performed using the Benjamini Hochberg false discovery rate.

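### The EEG mixed model states no baseline adjustment; constraining the arms to a common baseline mean would gain precision at no cost in data

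*Combined protocol and SAP*

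**What the plan says.** The Statistical analysis section treats the two outcome families differently.

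- **Cognition:** "General linear models (analysis of covariance) will be used to evaluate whether cognitive performance following all HD-tDCS sessions statistically differs between HD-tDCS conditions, covarying for" the pre-treatment score. A mixed model across the three assessments is added. The document history (version 0.4) records that ANCOVA replaced the mixed model as the primary analysis and that the mixed model became a sensitivity analysis.
- **EEG:** "EEG behavioral data will be tested using mixed effects models to examine for a significant interaction between HD-tDCS condition and time". Group is the between-subject factor; Time Point and task Condition are the within-subject factors. No baseline covariate and no equal-baseline constraint is stated. The section closes with a false discovery rate correction over electrode-time tests.

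The Design section has EEG collected at baseline, after session 10 and at two months. Target engagement by EEG is a secondary objective. The sample size paragraph gives its effect size and R² for the primary cognitive outcome only. For EEG it says "we expect the effect size of EEG outcomes to be at least equivalent to cognitive outcomes".

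**The concern.** Randomization makes the expected baseline means of the two arms equal. A group-by-time test in which baseline is one of the free outcome levels still estimates a separate baseline mean in each arm and subtracts the difference. That subtraction carries the full sampling error of the baseline means into the treatment contrast. Adjusting for baseline, or constraining the arms to share a baseline mean, removes only the part of the noise that baseline predicts.

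The plan makes this adjustment for cognition but not for EEG, where the mixed model is the only analysis named. With about 24 completers and a multiplicity correction to follow, the EEG analysis has little precision to spare. The stake is a greater chance of missing a real target-engagement signal.

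**Working it through.** **Inputs from the documents.** Allocation: "Participants will be randomized at a ratio of 1:1 to receive active 1 mA and sham conditions". Completers: 24 (Design), so 12 per arm. Significance level .05, taken as two-sided. Effect size f = .27, so d = 2 × .27 = .54 for two equal groups. Baseline R² = .2, so rho = √.2 = .447. Both f and R² are stated for the primary cognitive ANCOVA; using them for EEG is an assumption.

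**The plan's own figure.** The sample size paragraph says "A sample size of 20 provides 80% power to detect" f = .27. With noncentrality N·f²/(1−R²) = 20 × .0729/.8 = 1.82 on 1 and 17 df, power is 24.7%, not 80%. That is a separate issue, but it sets the scale of the power figures below.

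**Variance of a baseline-to-post contrast** (outcome variance 1 at each visit):

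- Free baseline (change score): 2(1−rho)
- Baseline adjusted: 1−rho²
- Ratio: (1−rho²)/[2(1−rho)] = (1+rho)/2, which is below 1 for every rho below 1

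So the direction does not depend on any borrowed input; only the size does. At rho = .447 the variances are 1.106 and .80, a ratio of .72.

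**Power at 24 completers, d = .54, rho = .447:**

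- Free baseline: noncentrality 24 × .0729/1.106 = 1.58 on 1 and 22 df; power 22.5%
- Adjusted: noncentrality 24 × .0729/.80 = 2.19 on 1 and 21 df; power 29.2%
- Gain: 6.7 points

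A simulation of 200,000 trials gives 22.7% and 28.4% (gain 5.7); a normal approximation gives 24.1% and 31.5% (gain 7.4). At N = 20 the exact figures are 19.3% and 24.7%.

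**Gain in percentage points over the unknown EEG correlation, 12 per arm:**

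| rho | d = .54 | d = .8 | d = 1.0 |
|---|---|---|---|
| .447 | 6.7 | 12.2 | 13.7 |
| .5 | 6.4 | 11.3 | 12.1 |
| .6 | 5.8 | 9.3 | 8.7 |
| .7 | 5.2 | 6.8 | 4.9 |
| .8 | 4.1 | 3.4 | 1.4 |
| .9 | 1.8 | 0.3 | about 0 |

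**Closer to the planned test.** The plan's interaction appears to span three visits. The table below uses a 2-df test on three visits, 12 per arm, rho = .447, compound symmetry and 2 and 44 df:

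| Effect at two months | Free baseline | Common baseline | Gain |
|---|---|---|---|
| Fully persists (.54, .54) | 22.3% | 33.3% | 11.0 |
| Halves (.54, .27) | 17.6% | 23.8% | 6.1 |
| Gone (.54, 0) | 22.3% | 25.0% | 2.8 |

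With 2 and 22 df the gains are 10.3, 5.7 and 2.6 points. Neither calculation includes the Condition factor or the false discovery rate correction.

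**The case against.** The strongest reply is that a group-by-time mixed model is valid under randomization: it is unbiased, keeps its error rate and is in common use. These are secondary outcomes in a small phase II trial, so the point concerns efficiency and not correctness. That stands, and nothing here says that the EEG test is wrong.

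Three further reservations also stand. The free baseline is inferred, because the section does not list the levels of Time Point for EEG. The sentence on the model names EEG behavioral data; its extension to spectral data is inferred from the electrode-time correction that follows it, and no other EEG model is given. The single-contrast figures are not for the exact planned test, which is why the three-visit figures are shown.

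A reader might go further in three ways that the documents do not support:

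- *That the plan's own inputs imply a loss of about 7 points for EEG.* R² = .2 belongs to the cognitive ANCOVA; no EEG correlation is given anywhere. For the same reason, one cannot say that the free-baseline contrast is worse than ignoring baseline: 2(1−rho) exceeds 1 only when rho is below .5.
- *That a larger EEG effect makes the gain larger.* This is true at rho = .447, but at rho = .8 the gain falls from 4.1 to 3.4 to 1.4 points as d rises from .54 to .8 to 1.0.
- *That the sample size paragraph promises EEG the power of an ANCOVA.* It speaks only of effect size.

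**Conclusion.** The point holds as an improvement that costs no data. The EEG model states no baseline adjustment, and adding one lowers the variance of the baseline-to-post group contrast at every correlation below 1. If EEG shared the cognitive f and R², single-contrast power at 24 completers would be about 29.2% instead of 22.5%. For d = .54 and rho from .5 to .9, the gain is 6.4 down to 1.8 points. For larger effects it ranges from about 14 points (d = 1.0, rho = .447) to almost nothing (d = 1.0, rho = .9). A 2-df three-visit test gains roughly 3 to 11 points at rho = .447 under compound symmetry, depending on how far the effect persists.

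These sizes rest on an assumed EEG effect and correlation, on baseline being a level of Time Point, and on no allowance for multiplicity. The adjustment does not bring power near 80% at f = .27 and R² = .2; that discrepancy lies in the sample size paragraph and needs its own answer.

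**What to change.** In the Statistical analysis section, list the levels of Time Point for the EEG models and constrain the two arms to a common baseline mean within each Condition. That means no group term at baseline, with group-by-post and group-by-two-month terms and their products with Condition retained. Test the post-treatment group differences from that model.

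A version with the participant's own baseline value as covariate (same task and Condition, and same electrode-time point for spectral data) is an alternative. It is not fully equivalent, because it drops participants without baseline EEG; the common-baseline model keeps them, in line with the plan's intention not to exclude participants for missing time points.

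State explicitly that the same rule applies to behavioral and spectral outcomes, and fix the wording before any unblinded EEG analysis. The cost is a few sentences and a changed design matrix. No new data are needed, and the only added assumption is the equality of baseline means that randomization provides.
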